8.2 Definition of an SAE

For each AE, you must determine if it is a serious adverse event (SAE) according to the following definition.

An SAE is an AE, occurring at any dose, which fulfills one or more of the following criteria:

- An event that results in death.
- An event that is immediately life threatening. This does not include an event that, had it occurred in a more serious form, might have caused death.
- An event that results in persistent or significant disability or incapacity.
- An event that is a congenital abnormality/birth defect
- An event that requires in-subject hospitalization or prolongs an existing
 hospitalization. Complications that occur during hospitalization and do not meet
 at least one of the above criteria for seriousness are AEs, not SAEs.
 Hospitalization means that the subject was formally admitted to the hospital, and
 does not include presentation at an emergency room.
- An event that, though not included in the above list, is an important medical event that may jeopardize the safety of the subject or may require medical or surgical intervention to prevent one of the outcomes listed above.

Medical and scientific judgment will be exercised in deciding whether a case is serious in those situations where important medical events may not be immediately life threatening or result in death, hospitalization, disability or incapacity. These include events that may jeopardize the subject or may require medical or surgical intervention to prevent one or

more outcomes listed in the definition of serious. Such events will usually be considered as serious. Examples of such events are:

- Angioedema not severe enough to require intubation but requiring intravenous hydrocortisone treatment
- Hepatotoxicity caused by paracetamol (acetaminophen) overdose requiring treatment with N-acetylcysteine
- Intensive treatment at the study site, in an emergency room, or at home for allergic bronchospasm
- Blood dyscrasias (e.g., neutropenia or anemia requiring blood transfusion) or convulsions that do not result in hospitalization
- Development of drug dependency or drug abuse (e.g., analgesics).

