8.7 Immediate Reporting of SAEs

ANY SERIOUS AE THAT OCCURS DURING THIS INVESTIGATION (SEE SECTION 8.2.), WHETHER OR NOT RELATED TO THE STUDY MEDICATION, MUST BE REPORTED IMMEDIATELY TO THE SPONSOR AND/OR THE DESIGNATED CRO.

The reporting timeframes and the required documentation for any SAE occurring during the study are summarized in Table 2.

In the event of an AE leading to hospitalization, every effort will be made by the investigational site to obtain a hospital discharge summary.

In the event of a fatal AE, documentation of any available postmortem findings, including autopsy, will be provided to ViroMed or their designee. In any event, the Investigator will provide a narrative summary of circumstances, events related to the death, and cause of death, if known.

Table 8-1 SAE Reporting Requirements

	Initial Reports	Follow-up Reports
	Fatal/Life Threatening	
Type of SAE	and all other SAEs	Any SAE
Timeframes	24 hours	As additional information become available.
Documents	24 hours: Completed initial SAE Report Form with minimum requirements (subject #, date of birth, event and start date)	Follow-up SAE Report Form and CRF documentation Hospital discharge summary Any relevant diagnostic test results/reports, including pathology reports Any postmortem findings/histopathology results

^a Within 24 hours after the site learns about the event.

NOTE: SAE = Serious Adverse Event.

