10.2 Adverse Events

All adverse event summaries will be restricted to Treatment Emergent Adverse Events (TEAE), which are defined as those AEs that occurred after dosing and those existing AEs that worsened during the study. Verbatim terms on case report forms will be mapped to preferred terms and system organ classes using the MedDRA dictionary (version 9.1).

Each adverse event summary will be displayed by dose cohort. Summaries that are displayed by system organ class and preferred terms will be ordered by descending order of incidence of system organ class and preferred term within each system organ class. Summaries of the following types will be presented:

- Subject incidence of TEAEs and total number of unique TEAEs by MedDRA system organ class and preferred term;
- Subject incidence of TEAEs by MedDRA system organ class, preferred term, and highest severity. At each level of subject summarization a subject is classified according to the highest severity if the subject reported one or more events. AEs with missing severity will be considered severe for this summary;

- Subject incidence of TEAEs by MedDRA system organ class, preferred term, and closest relationship to study drug (Related/Not Related). At each level of subject summarization a subject is classified according to the closest relationship if the subject reported one or more events. AEs with a missing relationship will be considered related for this summary;
- Subject incidence of serious TEAEs and total number of unique serious TEAEs by MedDRA system organ class and preferred term.

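### Protocol 8.2 contradicts itself on important medical events that arise during a hospital stay, and the SAP definition of a serious AE omits that criterion

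*Protocol*

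**What the plan says.** The lead-in to Protocol 8.2 classes an AE as serious if it is one "which fulfills one or more of the following criteria". Six bullets follow: death, immediate threat to life, disability or incapacity, congenital abnormality, hospitalization or prolongation, and important medical event.

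The fifth bullet opens with "An event that requires in-subject hospitalization or prolongs an existing" stay. It then adds a limiting sentence: "Complications that occur during hospitalization and do not meet" "at least one of the above criteria for seriousness are AEs, not SAEs".

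The sixth bullet comes after that sentence: "An event that, though not included in the above list, is an important medical event that may jeopardize the safety of the subject". The paragraph after the list leaves seriousness to medical judgment where the other outcomes have not occurred, and says of important medical events: "Such events will usually be considered as serious". It makes no exception for inpatients.

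Two later steps depend on the classification. Protocol 8.7 states: "ANY SERIOUS AE THAT OCCURS DURING THIS INVESTIGATION (SEE SECTION 8.2.), WHETHER OR NOT RELATED TO THE STUDY MEDICATION, MUST BE REPORTED IMMEDIATELY", with a 24-hour limit in Table 8-1. SAP 10.2 plans "Subject incidence of serious TEAEs and total number of unique serious TEAEs by MedDRA system organ class and preferred term", laid out as Table 15. The SAP's Definitions list gives five criteria for a serious AE, including prolongation of a hospital stay. Important medical event is not among them.

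**The concern.** The limiting sentence looks back to the criteria above it, and the important-medical-event criterion stands below. Read literally, an inpatient event that meets only the sixth criterion is excluded from SAE status by a flat rule written specifically for inpatients. A site coordinator could reasonably follow that rule as the more specific of the two.

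Seriousness decides whether the sponsor hears within 24 hours (Protocol 8.7), whether an event can qualify as an IND safety report (Protocol 8.9), and whether it enters the serious-event summary (SAP 10.2). Safety is the primary objective. Protocol 6.2.12 and 6.4.4 expect bypass, angioplasty or amputation to occur in some subjects, so hospital stays during follow-up are foreseeable. The error also runs in one direction: the sentence can remove SAE status but cannot add it.

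**Working it through.** No calculation applies to the wording itself. The check takes a complication that arises during a hospital stay and meets exactly one criterion of 8.2, and asks what each part of the section says about it.

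| Criterion met | Position relative to the limiting sentence | By the lead-in and list | By the limiting sentence |
|---|---|---|---|
| Death | above | SAE | SAE |
| Immediately life threatening | above | SAE | SAE |
| Disability or incapacity | above | SAE | SAE |
| Congenital abnormality | above | SAE | SAE |
| Prolongs the stay | above (preceding sentence, same bullet) | SAE | SAE |
| Important medical event only | below | SAE | AE, not SAE |

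One criterion of six is in conflict, and only for events during a hospital stay. The section's own examples show it. Angioedema treated with intravenous hydrocortisone without intubation is given as a serious event. If it arises in an inpatient and does not prolong the stay, the list says SAE and the limiting sentence says AE.

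**Comparison with the SAP.** The Definitions list names death, life-threatening experience, hospitalization or prolongation, disability or incapacity, and congenital anomaly. It agrees with the protocol on prolongation but leaves out important medical events for all subjects, not only inpatients. The SAP does not say whether Table 15 follows the investigator's classification under 8.2 or the SAP's own definition. If the SAP definition governs, these events are absent from Table 15 whatever 8.2 says.

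**Effect on Table 15 in a cohort of 3**, if the investigator's classification governs and one subject has one such event:

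- *An AE caused the admission.* That AE is already serious under the fifth bullet. Table 15 counts a subject once at each level, so the row for at least one serious event is 1/3 under either reading. The event count falls by one. The row for the reclassified preferred term falls from 1/3 to 0/3 if nothing else put the subject there.
- *The admission was not itself an SAE*, for example elective surgery for a pre-existing condition that had not worsened (Protocol 8.1), and the subject has no other serious event. Only then does the overall row fall, from 1/3 = 33% to 0/3 = 0%.

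**What does not depend on seriousness.** All AEs go on the CRF (Protocol 8.5). SAP 10.2 tabulates treatment-emergent AEs by severity and by relationship. The DSMC reviews all safety data (Protocol 9.4). The dose-limiting toxicity definition (Protocol 7.1.9) makes no use of seriousness, so the count that drives the maximum tolerated dose is unchanged.

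**The case against.** The strongest reply is that 8.2 can be read coherently. The sixth bullet is a residual category that comes after the limiting sentence, and failing the criteria above it is its condition of entry. The judgment paragraph confirms that such events are usually serious. On this view the limiting sentence says only that a complication is not serious merely because the subject is already in hospital. That is a sensible intention and probably what was meant. It stands to this extent: a reader might infer that the sentence cancels the sixth criterion, and the documents do not support that. Three parts of the section still make the event serious. What remains is a contradiction, because the sentence states its conclusion without exception and does not mention the criterion below it.

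A reader might also infer that complications prolonging a stay lose SAE status. That requires confining the word *above* to earlier bullets. Prolongation is stated immediately before the limiting sentence, and the SAP lists it as well, so this reading is not supported.

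The safeguards are real but partial. AE recording and DSMC review preserve the data, but the committee meets between cohorts and later at defined intervals. That does not replace a 24-hour report and does not correct Table 15.

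**Conclusion.** Wrong as written, as an internal contradiction; minor in severity. It affects in-hospital events that meet only the important-medical-event criterion, and only where the investigator follows the limiting sentence over the rest of 8.2. The exposure is a missed 24-hour report, a possible missed IND safety report if the event is also unexpected and reasonably possibly caused by the drug, and under-counting in Table 15 at event or preferred-term level. The SAP omission is a separate gap pointing the same way.

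The documents give no rate of admission or of such complications. One could assume that 3 to 6 of 12 subjects are admitted and that 20 to 50% of those have a prolonging or medically important complication, which gives 3 × 0.2 = 0.6 to 6 × 0.5 = 3 events. That range should not be used. Both inputs are invented, prolonging events are not affected, and it supposes that every affected event is misclassified. Nor should a fall from 33% to 0% in a cohort be taken as the usual effect, since it needs an admission that was not itself an SAE and no other serious event in that subject. The finding rests on the text and does not depend on either figure.

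**What to change.** Two changes, made together:

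- In Protocol 8.2, have the limiting sentence refer to complications that do not meet *any of the criteria for seriousness in this section (including important medical event)*, in place of its present reference to the criteria above.
- In the SAP's Definitions list, add the important-medical-event criterion to the definition of a serious AE, so that expedited reporting and Table 15 use the same rule.

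The cost is one phrase in the protocol and one criterion in the SAP. No assessment, dose or clinical rule changes. The number of reported SAEs may rise slightly.

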8.3 Laboratory AEs and SAEs

Abnormal laboratory findings (e.g., serum chemistry, hematology) or other abnormal assessments (e.g., ECGs, vital signs) that are judged by the Investigator to be clinically significant must be recorded as AEs or SAEs if they meet the definition of an AE or SAE, as defined in Sections 0 and 8.2, respectively. Clinically significant abnormal laboratory or other assessment findings that are detected following study drug administration or that are present at Baseline and worsen following the start of the study constitute AEs or SAEs. The Investigator will exercise clinical judgment in deciding whether an abnormal laboratory finding or other abnormal assessment is clinically significant.

8.4 Detection of AEs and SAEs: Method, Frequency, and Time Period

The methods of detection for AEs and SAEs include, but are not limited to, the use of non-leading verbal questioning of the subject (e.g., how do you feel?), clinical observation by the Investigator or study staff, physical examinations, monitoring of vital signs, or laboratory assessments.

AEs will be recorded for each subject from the time the subject signs the informed consent form through the subject's final follow-up visit. AEs and SAEs that result from study participation and occur prior to the start of the study drug will be recorded.

8.5 Documentation of AEs and SAEs

All AEs occurring during the study must be recorded in the subject's medical records and on the AE page of the CRF, even if the AE is considered by the Investigator to be unrelated to the use of the study drug. SAEs that occur during the study must be documented in the subject's medical record, on the AE page of the CRF, and on the SAE Report Form.

A separate SAE CRF will be used for all SAEs. For SAEs which are related and within a specific time period, a single form can be used. An assessment of the relationship of each event to the study therapy will be added for each SAE on the form. Following initial reporting of the event, the Investigator will make every effort to establish a diagnosis of the event based on the presenting signs, symptoms, and/or other clinical information. In such cases, the diagnosis will be documented as the AE and/or SAE and not the individual signs/symptoms.

Death will not be reported as a serious adverse event. Death will be reported as the outcome of the event. When a subject expires, please use the cause of Death (acute MI, CVA, sepsis) as the SAE and the outcome as Death. When no cause of Death is apparent, please use cardio-pulmonary arrest as the SAE.

If a clinically significant, abnormal laboratory finding or other abnormal assessment meets the definition of an AE or SAE, then the AE page of the CRF and the SAE Report Form must be completed, as appropriate. A diagnosis, if known, or clinical signs and symptoms if the diagnosis is unknown, rather than the clinically significant abnormal laboratory finding, will be recorded on the AE page of the CRF and on the SAE Report Form, as appropriate. If no diagnosis is known and clinical signs and symptoms are not present, then the abnormal finding will be recorded. If an isolated laboratory abnormality is an SAE, then the following will be performed: 1) the laboratory data will be recorded in the SAE Report Form with the reference range and all preceding measurement(s) value(s), including Baseline value(s), and 2) copies of the laboratory reports and reference ranges will be sent with the SAE Report Form.

The SAE CRF used to report an SAE will be completed as thoroughly as possible and signed by the Investigator or designee before transmittal. The Investigator must provide the relationship of the event to the study drug (assessment of causality to the trial medication), action taken with the study drug and outcome (if known) at the time of the initial report. SAE CRFs will be sent via Datafax to: [contact].

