6.3 Autopsy

In the event of the death of the study subject, the investigator will be required to request an autopsy from the family of the deceased. An autopsy will assist ViroMed in learning more about the safety and efficacy of gene transfer. If an autopsy is performed, the final autopsy report will be included in the subject's study file and a copy of the report will be sent to both ViroMed and the designated Clinical Research Organization (CRO). The refusal of the family to permit an autopsy will be documented in the study subject's file and on the CRF.

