| | Results/ Pregnancy Outcome | |
| 7 | Ulcer Measurements | 16 |
| 8 | High Resolution MRA/ Injection Site Reaction | 16 |
| 9 | Assessment of CLI | 17 |
| 10 | Hemodynamic Assessments | 18 |
| 11 | Visual Analogue Scale for Pain | 19 |
| 12 | Transcutaneous Oxygen Pressure Assessment- TcPO ₂ | 19 |
| 13 | Concomitant Medications Identified as being Analgesic in | 98 |
| | Nature | |
| 14 | Study Drug Administration | 20 |
| 15 | Adverse Events | 97 |
| 16 | Serious Adverse Events | 97 |
| 17 | Hematology | 11 |
| 18 | Chemistry | 12 |
| 19 | Urinalysis | 13 |
| 20 | Physical Examinations | 7,8 |
| 21 | Vital Signs | 9 |
| 22 | Retinal Fundoscopy/ Chest X-Ray/ CT Scan | 10 |
| 23 | Infection Tests | 14 |
| 24 | Tumor Markers | 15 |
| 25 | Concomitant Medications | 98 |
| 26 | VM202 DNA Levels (include Collection Date/Time from CRF) | 16, Lab |
| 27 | Endothelial Progenitor Cell Assay | 14 |
| 28 | Serum HGF/ Anti HGF Antibodies (include Collection | 14, Lab |
| | Date/Time from CRF) | |
| 29 | Telephone Follow-Up Contact | 22 |
| 30 | Waiver | 23 |

List of Data Listings (cont)

| Listing | | CRF |
|---------|---------------------|----------|
| Number | Listing Description | Plate(s) |
| 31 | Death | 101 |

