| | Number of | Number of | Number of | Number of | Number of | Number of | Number of | Number of |
| System Organ Class / Preferred Term | Subjects [1] | Events | Subjects [1] | Events | Subjects [1] | Events | Subjects [1] | Events |
| Subjects Reporting at Least One Adverse Event | n (%) | n | n (%) | n | n (%) | n | n (%) | n |
| System Organ Class 1 | n (%) | n | n (%) | n | n (%) | n | n (%) | n |
| Preferred Term 1 | n (%) | n | n (%) | n | n (%) | n | n (%) | n |
| Preferred Term 2 | n (%) | n | n (%) | n | n (%) | n | n (%) | n |
| | | | | | | | | |
| • | | | | | | | | |
| System Organ Class 2 | n (%) | n | n (%) | n | n (%) | n | n (%) | n |
| Preferred Term 1 | n (%) | n | n (%) | n | n (%) | n | n (%) | n |
| Preferred Term 2 | n (%) | n | n (%) | n | n (%) | n | n (%) | n |

[1] At each level of summation (overall, system organ class, preferred term), subjects reporting more than one adverse event are counted only once.

Protocol Number: US-06-1-001

Table 13
Treatment Emergent Adverse Events by System Organ Class and Severity [1]
Safety Population
Part 1 of 2

| | VM202-2 mg (N=) | | | | | VM202-4 mg (N=) | | | | |
|--|-------------------------|-------------------------|-------------------------|-------------------------|-------------------------|-------------------------|-------------------------|-------------------------|-------------------------|-------------------------|
| System Organ Class / Preferred Term | Mild | Moderate | Severe | Life Threat. | Death | Mild | Moderate | Severe | Life Threat. | Death |
| Subjects Reporting at Least One Adverse Event | n (%) |
| System Organ Class 1 | n (%) |
| Preferred Term 1 | n (%) |
| Preferred Term 2 | n (%) |
| | | | | | | | | | | |
| - | | | | | | | | | | |
| System Organ Class 2 Preferred Term 1 Preferred Term 2 | n (%) n (%) n (%) |

^[1] At each level of summation (overall, system organ class, preferred term), subjects reporting more than one adverse event are counted only once using the highest severity.

Protocol Number: US-06-1-001

Table 13
Treatment Emergent Adverse Events by System Organ Class and Severity [1]
Safety Population
Part 2 of 2

| | VM202-8 mg (N=) | | | | | VM202-16 mg (N=) | | | | | |
|---|------------------|----------|--------|--------------|-------|-------------------|----------|--------|--------------|-------|--|
| System Organ Class / Preferred Term | Mild | Moderate | Severe | Life Threat. | Death | Mild | Moderate | Severe | Life Threat. | Death | |

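### Deaths with no apparent cause are coded as cardio-pulmonary arrest, so the safety tables merge them with documented arrests and no planned table counts them separately

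*Protocol*

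**What the plan says.** Protocol 8.5 treats death as an outcome and not as an event term: "Death will not be reported as a serious adverse event. Death will be reported as the outcome of the event". The site reports the cause of death as the serious event. For a death without a known cause the instruction is: "When no cause of Death is apparent, please use cardio-pulmonary arrest as the SAE".

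For abnormal laboratory or other findings, the same section takes a different approach: "If no diagnosis is known and clinical signs and symptoms are not present, then the abnormal finding will be recorded".

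Protocol 6.3 requires the investigator to request an autopsy and provides for the family declining: "The refusal of the family to permit an autopsy will be documented in the study subject's file and on the CRF". Protocol 8.6 lets the SAE form be updated as information arrives. Protocol 8.7 asks for a narrative of every fatal event, with the cause if it is known.

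SAP 10.2 maps the site's verbatim terms to MedDRA preferred terms and system organ classes. For serious events it plans: "Subject incidence of serious TEAEs and total number of unique serious TEAEs by MedDRA system organ class and preferred term". The Table 13 layout splits each preferred term by severity under the columns "Mild | Moderate | Severe | Life Threat. | Death". SAP Appendix A also plans a listing of serious adverse events (Listing 16) and a listing of deaths (Listing 31, from its own CRF page).

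**The concern.** The rule makes the site name a specific event in exactly the situation where it does not know what happened. That term is then coded and counted like any observed event. Incidence of adverse events through Day 365 is the first primary safety endpoint in Protocol 4.1.1, so the substitution reaches the main output of the trial.

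The situation is foreseeable. Subjects may be up to 90 years old (Protocol 5.2). Life expectancy is an exclusion only when it is below 6 months (5.3), yet follow-up runs to Day 365 (4.6). An autopsy may be refused (6.3).

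Two things are at stake. The tables could show an arrest at a dose level where nobody documented one. A reader of the tables also could not tell how many deaths in a cohort were unexplained. In addition, 8.5 asks the investigator to judge relationship to study drug in the initial report, and for these deaths that judgement attaches to the assigned term.

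**Working it through.** The documents give no figure to reproduce. The check follows one death of unknown cause, occurring after dosing, from the site to the tables.

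1. **Site (Protocol 8.5).** Death may not be the event term and no cause is known. The event entered is cardio-pulmonary arrest, outcome death.
2. **Coding (SAP 10.2).** The verbatim term is what gets coded. The coded record carries the arrest term and nothing in the SAP marks it as a default.
3. **Tables 12, 14 and 15.** The subject is counted on the arrest row. A count of one there fits three different histories: an unexplained death, a death for which the investigator named a documented arrest as the cause, or an arrest that the subject survived.
4. **Table 13.** The Death column removes the survived arrest. The other two histories still share the cell.
5. **Other tables.** Table 1 has no death row among its discontinuation reasons. No table in SAP Appendix A or B has a line for deaths of unknown cause.
6. **Listings.** Listings 16 and 31 show the individual cases. The columns of Listing 31 and the content of the Death CRF page are not given, so whether they record an unknown cause cannot be determined.

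**Contrast within 8.5.** With no diagnosis and no symptoms, a laboratory abnormality is recorded as the abnormality, which is what is known. With no cause, a death is recorded as a named event, which is not known.

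**Size.** Assume one unexplained death and no other arrest in a cohort. Cohort sizes come from Protocol 4.3 and 6.1.1: 3 subjects, or 3 + 3 = 6 after a dose-limiting toxicity. Incidence = subjects on the row / cohort size.

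| Cohort | Arrest row, as written | Arrest row, after fix | Unknown-cause row, after fix |
|---|---|---|---|
| 3 | 1/3 = 33.3% | 0/3 = 0% | 1/3 = 33.3% |
| 6 | 1/6 = 16.7% | 0/6 = 0% | 1/6 = 16.7% |

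The number of subjects with a serious event and the number of deaths are the same either way; only the label moves. The 33.3 and 16.7 points are simply the weight of any single event in a cohort of that size.

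**The case against.** A reader might infer that unexplained deaths disappear from the report or are concealed from the safety committee. The documents do not support that. Fatal events appear in Table 13, Listing 16 and Listing 31. Each has a narrative, an autopsy request and an updatable SAE form. With 12 to 15 subjects, deaths would in practice be read one by one. Protocol 9.4 gives the committee all safety data, including outcome, and nothing restricts it to the SAP tables.

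A second argument has real force. Because 8.5 sends every death with a known cause to that cause, a fatal arrest entry is mostly a marker of unknown cause. The arrest row of Table 13's Death column therefore approximates the missing count. The approximation fails when an investigator names a documented arrest as the cause. It also relies on fatal events being graded in the Death column, although the severity definitions in Protocol 8.1 stop at severe, beside a reference to the CTCAE grades.

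Third, no rule set out in these documents turns on the label. The dose-limiting toxicity definition in Protocol 7.1.9 covers anaphylaxis, fever and injection-site necrosis, and SAP 8.5 plans no formal cohort comparisons. This stands, with one limit: Protocol 9.4 mentions pre-specified stopping rules kept in a separate committee document, which cannot be checked here.

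What survives is narrower. The summary tables report an event that may not have been observed, and they do not count unexplained deaths. Updating the SAE form cures this only when a cause is later found. Otherwise the reader must use narratives to override the coded data.

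**Conclusion.** The point holds as a matter of accurate recording and tabulation. Following Protocol 8.5 and SAP 10.2 as written merges unexplained deaths with documented arrests in Tables 12 to 15, and no planned table separates them. One such death would show as 33.3% cardio-pulmonary arrest in a cohort of 3, or 16.7% in a cohort of 6. Death and serious-event totals do not change, and neither dose escalation nor the MTD as described in the protocol is affected.

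This assumes that at least one treatment-emergent death without an apparent cause occurs, that sites follow 8.5 literally, and that no cause is established later. How many such deaths to expect cannot be estimated from the documents. If the Death CRF page and Listing 31 already carry a field for unknown cause, the gap is confined to the summary tables.

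**What to change.** Amend both sentences in Protocol 8.5, because changing only the second would leave the section contradicting itself. Suggested text: 'Death is recorded as the outcome of the event that caused it. When no cause is known, the event term is: death, cause unknown, with outcome death. The term is updated if autopsy or medical records establish a cause. Cardio-pulmonary arrest is used only when an arrest is documented.'

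Carry the same wording into the SAE form instructions. In the SAP, show deaths of unknown cause by cohort, either as a line in Table 15 or as a column in Listing 31.

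The cost is a small edit to the SAE instructions and one table or listing line. Any death already reported under the default term would need its term checked against the narrative. No change to the design, sample size or visit schedule is needed.
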